10.5. Randomization and Blinding

Part 1: This is an open-label, dose escalation phase that does not require randomization.

Part 2: Patients who have signed the informed consent and meet all eligibility criteria will be stratified by CMT disease type (CMT1 or CMTX) and then randomized to receive ACE-083 (at a dose level determined by Part 1) or placebo. The randomization scheme will be computer generated and will be prepared by a statistical group designated by the sponsor.

If a patient discontinues the study for reasons other than a safety issue related to ACE-083 and the patient had not completed visit Day 43, the patient may be replaced. The replacement patient will receive the same treatment as the patient replaced. Both the replacement and originally allocated patient numbers will be unique numbers.

Among study personnel, only the pharmacist or his/her designee who prepares the study drug (ACE-083 or placebo), an unblinded clinical monitor designated by the sponsor, and the analytical laboratory will be unblinded to the patient treatment assignments. All other study personnel (including but not limited to investigators, study coordinators, nursing staff, and clinical monitors) and all patients will remain blinded to the study treatment assignments. The sponsor and the sponsor's representatives will also remain blinded to the study treatment assignments.

In the event of a medical emergency for an individual patient in which knowledge of the study drug is critical to the patient's medical management, the investigator may break the blind for that patient. However, prior to breaking the blind, every effort must be made by the investigator to first discuss the need to break the blind with the medical monitor. Further, it must be determined

09 January 2019 Acceleron Pharma Inc. Clinical Study Protocol Study A083-03 Revision: 03 by the investigator that b

by the investigator that breaking the treatment blind is necessary information for the medical management of that patient. If the blind is broken prior to Day 190, the patient must be withdrawn from the study and complete the tests and evaluations scheduled for the end of treatment visit (Day 358/ET) and will be expected to return to the clinic to complete the remaining follow-up visit assessments.

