**Table 1: Planned Doses to be Administered for Part 1**

Cohort	Dosing Days	Muscle	Planned Dose Level	Type of Administration	ACE-083 n
1	1, 22, 43, 64, and 85	Tibialis Anterior	150 mg	Bilateral	6
2	1, 22, 43, 64, and 85	Tibialis Anterior	200 mg	Bilateral	6
3	1, 22, 43, 64, and 85	Tibialis Anterior	240 mg	Bilateral	6
Total Number of Patients (Planned)					18

Periodic reviews of selected blinded safety and imaging data will be reviewed by the Safety Review Team (SRT) in accordance with the SRT Guidelines.

#### 3.2. Part 2

Prior to the initiation of Part 2, a review of the safety and efficacy data from Part 1 will be done in order to determine the recommended dose level. Up to 40 patients will be enrolled and randomized (1:1 ratio) to receive either ACE-083 (n=20) or placebo (n=20) bilaterally. Patients will receive study drug once every three weeks for approximately 6 months (9 doses). If a patient discontinues the study for reasons other than a safety issue related to investigational study drug and the patient had not completed the Day 43 visit, the patient may be replaced. The replacement patient will receive the same treatment as the patient replaced.

Patients who complete the double-blind treatment period will immediately roll over to open-label treatment with ACE-083. All patients will receive ACE-083 administered at the same dose as in the double-blind period. They will receive bilateral injections, once every three weeks for approximately 6 months (8 doses). In Part 2, the SRT will periodically review the blinded safety data.

A stratified randomization schedule will be prepared under the direction of the Sponsor with the stratification factor of “CMT disease type” (values are CMT1 and CMTX). Because Part 2 is multicenter, an Interactive Response Technology (IRT) system will be used to randomize patients sequentially across clinical sites.

Similar to Part 1, periodic reviews of selected blinded safety and imaging data will be reviewed. Further details concerning the frequency and timing of SRT reviews of Part 2 data are described in the SRT Guidelines.

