### 4.1.5. Data Handling Conventions

Unless otherwise stated or indicated:

- Individual data for all patients will be presented in data listings, sorted by “Study Part” (Part 1 or Part 2), “Treatment Group”, and “Patient Number”;
- For any parameter analyzed, only observations from visits and/or time points planned in the protocol will be used in descriptive statistics. An exception to this rule is for a baseline assessment. Should an unscheduled assessment be taken after the scheduled baseline assessment but before the first dose of study medication, then the unscheduled assessment may be used as the baseline;
- For variables where the Day 1 assessment is defined as the baseline, should an individual patient have a Day 1 assessment after having received their first dose, then an unscheduled assessment may be used as the baseline, provided that the unscheduled assessment was done prior to first dose.
- Should a patient be assigned to the wrong CMT-type stratum (e.g. a CMT1 patient assigned to the CMTX stratum or a CMTX patient assigned to the CMT1 stratum), the patient’s true CMT-type (CMT1 or CMTX) will be used in statistical models where CMT-type is used as a covariate.
- With the exception of what is described in the preceding bullet, unscheduled assessments will not be collectively summarized in summary tables or figures; however, these data will appear in individual patient listings.
- For adverse events where the assessment of “Relationship to study drug” is missing, it will be assumed that the adverse event is “Probably Related” to study drug.
- For selected pharmacodynamic and efficacy data, tests of statistical hypotheses and estimation using the end-of-treatment visit or the Day 190 visit (Part 2 double-blind component), multiple imputation for missing data will be performed. Additional techniques for handling missing data may also be considered and evaluated.
- If a patient has a Day 190 assessment performed after having received the Day 190 dose (first dose in the open-label phase), then the Day 190 assessment for that patient will be included in statistical analyses of Day 190 data only if the difference between the Day 190 assessment and the Day 190 dose date is less than or equal to 7 days.
- Descriptive statistics for quantitative parameters will be provided using number of observations (N), mean, standard deviation (SD), standard error of the mean (SEM), median, minimum and maximum;

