## 4.2. Analysis Population

The analysis populations include the following:

- Full Analysis Set: Part 1 – All patients enrolled in the study receiving at least one dose of ACE-083. Part 2 – All patients randomized who have received at least one dose of study drug (includes placebo);
- Safety Set: All patients enrolled/randomized in the study who have received at least one dose of study drug (includes placebo);
- Per Protocol Set: All patients enrolled/randomized in the study who have received at least one dose of study drug (includes placebo) with no data or study procedural related issues that would otherwise impact the interpretability of the efficacy and/or pharmacodynamic data.

Such issues include but are not necessarily limited to:

- Patients who discontinue the study prior to the Dose 3 Day 43 visit; these patients may have been replaced per protocol
- Patients whose Day 1 MRI or Day 190 MRI was done 7 or more days following study drug administration
- Patients who did not receive the full study drug administration planned per protocol at all injection sites on any or both sides (right or left) for 2 or more consecutive visits for reasons other than dose reductions for the safety of the patient or feasibility concern (i.e., the site intended to administer the full dose but was unable).

- Patients whose Screening cumulative distance walked at 6 minutes is greater than 500 meters or less than 150 meters.

A review of the patient data will be performed and a list of patients to be excluded from the Per Protocol Set along with the reason for exclusion will be completed before the data is locked and unblinded.

Statistical analyses of efficacy and pharmacodynamics data will be performed on the Per Protocol Set (primary analysis population) and the Full Analysis Set (secondary analysis population). Analyses of safety data will be performed on the Safety Set. Should the statistical analysis populations be identical (e.g., Full Analysis Set = Per Protocol Set), statistical analyses will not be duplicated or repeated.

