### **4.8.2.2. Part 2**

#### **4.8.2.2.1. Double-Blind Period**

##### **MRI: Total Muscle Volume (TMV)**

Individual total muscle volume data will be listed.

Descriptive statistics will be provided by treatment group and scheduled time for raw data and changes from baseline (absolute and percent change) for each side [left and right]. The average absolute change and average of the percent change for the left and right sides will also be provided.

The primary pharmacodynamic analysis will consist of an ANCOVA in order to assess the effect of ACE-083 on the Day 190 average percent change from baseline for the left and right sides. Covariates to be included into the model are TREATMENT, BASELINE, and CMT-TYPE where:

- TREATMENT represents the treatment group (ACE-083 or placebo)
- BASELINE represents the baseline total muscle volume (average of left and right sides)
- CMT-TYPE refers to the type of CMT (e.g. CMT1 or CMTX)

The effect of ACE-083 versus placebo will be estimated using the ANCOVA model described above and tested using a 0.1 significance level (2-sided). The least-square mean estimate along

with the corresponding 90% confidence interval will be provided. In addition, the 95% confidence interval will also be provided.

If the Day 190 TMV has no missing data, then the above ANCOVA model will be used for analysis. If missing data is present, a standard multiple imputation with the above ANCOVA model will be used for analysis as described in [Section 4.11.1](#).

A mixed model repeated measures (MMRM) analysis will be performed to assess the sensitivity to the ANCOVA analysis described above. An unstructured covariance structure will be used to model the within-patient covariance across visits. Other covariance structures will be considered if the unstructured covariance fails. The covariates to be included consist of all of the covariates described above for the ANCOVA with the addition of the following additional covariates: VISIT where VISIT represents the scheduled visit day post first dose of MRI assessment and TREATMENT\*VISIT.

Similar to what was described for the ANCOVA analysis above, if missing data is present, a standard multiple imputation with the above MMRM model will be used for analysis as described in Section 4.11.1.

The statistical analyses described above will be done on the Per Protocol Set and will be considered primary. The analyses described above will also be repeated for the Full Analysis Set.

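### The Part 2 primary test of muscle volume is run on a Per Protocol Set that drops every patient leaving before Day 43, whatever the reason

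*SAP*

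**What the plan says.** The Part 2 primary objective is superiority: whether ACE-083 increases TMV over placebo. SAP 4.2 sets the population for all efficacy and pharmacodynamic analyses: "Statistical analyses of efficacy and pharmacodynamics data will be performed on the Per Protocol Set (primary analysis population"), with the FAS secondary. The TMV section of SAP 4.8.2.2.1 repeats it: "The statistical analyses described above will be done on the Per Protocol Set and will be considered primary". The TMV analysis is then rerun on the FAS.

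The PPS exclusions are introduced with "Such issues include but are not necessarily limited to", so the list is open. The first is "Patients who discontinue the study prior to the Dose 3 Day 43 visit", with no restriction by reason. The replacement rule does restrict by reason. Protocol 10.5 allows replacement only when a patient "discontinues the study for reasons other than a safety issue related to ACE-083", and SAP 3.2 says the same ("for reasons other than a safety issue related to investigational study drug").

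Protocol 14.1 defines the Part 2 FAS as all randomised patients; SAP 4.2 also requires at least one dose. SAP Section 5 lists the new PPS definition but not the new FAS definition, although SAP 4.1.4 still sets a baseline date for randomised patients who were never dosed. The protocol names no primary population, so choosing the PPS contradicts nothing in it. The list of patients excluded from the PPS is to be settled before lock and unblinding.

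**The concern.** Leaving before Day 43 happens after randomisation and after one or two doses. If ACE-083 changes who leaves, through injection reactions or perceived lack of benefit for example, the patients left in the two PPS arms are no longer the groups that randomisation made comparable. The primary estimate and p-value then carry that selection.

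The replacement rule shows the gap. A patient who leaves before Day 43 because of a drug-related safety issue is not replaced, and the PPS rule removes the same patient from the primary analysis.

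Two smaller faults sit in the same section.

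- The PPS excludes a screening 6-minute walk distance above 500 m in both study parts, but Part 1 eligibility (Protocol 8.1) has no upper limit. An eligible Part 1 patient could be dropped from the main analyses of the secondary efficacy and PD endpoints, and one patient is 1 of 6 in a cohort.
- The late-scan rule, "Patients whose Day 1 MRI or Day 190 MRI was done 7 or more days following study drug administration", meets SAP 4.1.5, which admits a late Day 190 assessment "only if the difference between the Day 190 assessment and the Day 190 dose date is less than or equal to 7 days". A scan at exactly 7 days is usable under one rule and removes the patient under the other.

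The exclusion for incomplete injections exempts safety reductions and feasibility problems, and the late-scan rule targets contaminated scans. The main argument relies on neither.

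**Working it through.** **The plan's own figure.** Inputs (SAP 4.1.1): difference 10 points, SD 10, two-sided alpha 0.10, 1:1 allocation, 90% power. With a two-sample t-test (noncentral t), 17 per arm gives 88.7% and 18 per arm gives 90.2%, so 36 evaluable patients is right. Allowing 10% dropout, 36/0.9 = 40. The arithmetic stands; the question is only who is analysed.

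**Bias from one-sided exclusion (illustration).** Assumptions not in the documents: 20 randomised per arm, no true effect, no placebo exclusions, SD 10 among those retained, and k ACE-083 patients excluded who average L SDs below their whole-arm mean. The retained ACE-083 mean then sits above the whole-arm mean by

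bias = 10 × L × k/(20 − k).

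Type I error comes from the noncentral t with 20 − k against 20 patients and noncentrality bias / [10 × √(1/(20 − k) + 1/20)]. For k = 2, L = 1: bias = 10 × 2/18 = 1.11; standard error = 10 × √(1/18 + 1/20) = 3.25; noncentrality = 0.342.

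| k of 20 | L | Bias (points) | Two-sided type I error | False wins for ACE-083 (nominal 5%) |
|---|---|---|---|---|
| 1 | 0.5 | 0.26 | 10.1% | 5.9% |
| 1 | 1 | 0.53 | 10.4% | 6.9% |
| 2 | 0.5 | 0.56 | 10.5% | 7.0% |
| 2 | 1 | 1.11 | 11.9% | 9.5% |
| 4 | 0.5 | 1.25 | 12.3% | 10.0% |
| 4 | 1 | 2.50 | 18.9% | 18.0% |

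The plan's 10% allowance corresponds to k = 2 (0.10 × 20), so the k = 4 rows lie beyond it. With the same exclusions in both arms (k = 2, L = 1 in each), type I error stays at 10.0%. If leavers were better than their arm, the bias would have the same size in the other direction.

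**What the FAS would show.** Suppose 2 of 20 ACE-083 patients leave early and would gain 0, the other 18 gain 10, and placebo gains 0. The PPS difference is 10.0. The FAS difference depends on how the two are handled:

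- their zero gain is observed and used: (18 × 10 + 2 × 0)/20 = 9.0;
- imputed without treatment arm, pooled mean 180/38 = 4.74: (180 + 2 × 4.74)/20 = 9.47;
- imputed under missing at random (MAR) with treatment arm and no post-baseline data: about 10.0, the same as the PPS.

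SAP 4.11.1 imputes from earlier time points and does not say whether treatment arm is in the model, so the documents do not settle which applies. The first scheduled post-baseline MRI is Day 43, and Protocol 9 waives the withdrawal MRI if one was done within 4 weeks. An early leaver may therefore have no later scan.

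**Power after the change.** With 20 per arm: 92.8% at 10 points and 87.5% at 9 points.

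**The case against.** The strongest reply concerns size. Within the dropout allowance, two-sided type I error reaches at most 11.9%, and that requires an arm's whole allowance for the double-blind period to be spent before Day 43, on ACE-083 only, by patients 1 SD worse than their arm. No passage links early leaving to smaller muscle gain, so the direction is assumed. Protocol 10.1.1 narrows the routes out: after a grade 3 or higher event, discontinuation by rule follows only when dosing has not resumed within 6 weeks of the last dose, which is Day 43 at the earliest. The Phase 1 study reported no serious or grade 3 or higher events. Exclusions are fixed before unblinding, and the FAS rerun is already planned. Under MAR with treatment arm, moving to the FAS may give almost the same answer.

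Most of this is accepted. The bias may be small, its direction is unknown, and relabelling alone may not move the estimate. Three things remain. The 6-week rule closes one exit, while patient request and other adverse-event withdrawals stay open. Fixing exclusions blind prevents selective choice but does not restore comparability when treatment affects who leaves. The limit of MAR is a reason to specify the imputation and add a sensitivity analysis; it does not justify a primary set that omits these patients.

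The side points are also fairly called minor. The two 7-day rules govern different things (use of a scan, membership of a set) and differ only at the boundary. Randomisation falls within 24 hours before the first dose, so few patients should be randomised and undosed. The documents do not show that any Part 1 patient walked more than 500 m.

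**Conclusion.** The concern holds and should be fixed. The Part 2 superiority test is assigned to a population defined partly by a post-randomisation event that treatment can affect. The all-randomised comparison is secondary, and its definition is narrowed without an entry in Section 5. The text is clear on each of these; the size of the bias is not known. The illustrative 0.3 to 1.1 points, with two-sided type I error of 10.1% to 11.9%, rests on exclusions in the ACE-083 arm only, leavers 0.5 to 1 SD below their arm, and no more than 2 of 20 excluded. The range is 12.3% to 18.9% at 4 of 20, and there is no inflation if exclusions match across arms.

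**What to change.** - In SAP 4.2 and 4.8.2.2.1, make the protocol's Part 2 FAS (all randomised, analysed as randomised) primary for efficacy and pharmacodynamic data, using the planned multiple imputation. Keep the PPS as supportive, with a closed exclusion list.
- In SAP 4.11.1, state that treatment arm and any early-termination MRI enter the imputation model. Add one sensitivity analysis that imputes early ACE-083 leavers from the placebo arm.
- Treat a Day 190 MRI outside the SAP 4.1.5 window as missing instead of removing the patient, and use one 7-day cut-off in both places.
- Apply the 150 to 500 m walk-distance exclusion to Part 2 only.
- If the dosed-only FAS is kept, list it in SAP Section 5.

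The cost is SAP wording and one added sensitivity run. The estimate may be slightly smaller: if 2 of 20 ACE-083 patients gain nothing and this is reflected in the analysis, power is 87.5%, against 90.2% for the planned 18 per arm at 10 points. Patients without a post-baseline scan will be carried by imputation.

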#### **4.3. Subject Disposition**

Individual patient disposition data will be listed.

Frequency counts will be tabulated for disposition data and will include the following:

- Number of patients enrolled [Part 1 only],
- Number of patients randomized [Part 2 only],
- Number (%) of patients completing the study [Part 1 only],
- Number (%) of patients completing the double-blind treatment period [Part 2 only]
  - A patient is said to have completed the double-blind treatment period if the patient completed up to and including the Day 190 visit.
- Number (%) of patients entered into the open-label period [Part 2 only]
- Number (%) of patients completing the open-label treatment period [Part 2 only]
  - A patient is said to have completed the open-label treatment period if the patient completed up to and including the Day 337 visit.
- Number (%) of patients that rollover to the extension study, A083-04
  - Patients that rollover to the extension study consist only of patients participating in Part 2 of this study who complete both the double-blind treatment period AND the open-label treatment period who will not have the Day 393/EOS visit. These patients' final study visit will be the Day 358/ET visit.
- Number (%) of patients that do not rollover to the extension study A083-04
  - Patients that do not rollover to the extension study will have both the Day 358/ET and Day 393/EOS visits completed.
- Number (%) of patients discontinuing from the study prior to completing both the double-blind period and the open label period [Part 2 only]
  - Number (%) of patients that discontinued during the double-blind period
  - Number (%) of patients that discontinued during the open-label period

- Number (%) of patients for primary reason for discontinuation will also be provided [provided there is at least one patient who discontinued].

Summaries will be provided by treatment and overall for each study part (Part 1 and Part 2).

## 4.4. Demographic and Baseline Characteristics

### 4.4.1. Demographics

Individual demographic data will be listed.

Descriptive statistics (N, mean, SD, median, minimum and maximum) will be provided for continuous demographic variables (age, weight, height, and BMI) and frequency counts will be tabulated for categorical demographic variables (gender, race, ethnicity) by treatment and overall for each study part (Part 1 and Part 2). Age will be calculated based on birth date and informed consent date.

### 4.4.2. Baseline Characteristics

Baseline characteristics of the patient population consist of selected items from the CMT disease history, MRI, MRC-MMT, and functional test data. Such data includes the following:

- Age at onset of symptoms (years)
- Age at diagnosis (years)
- Duration since onset of symptoms (years)
  - Duration since onset of symptoms = Age (years) – Age at onset of symptoms (years)
- Duration since diagnosis (years)
  - Duration since diagnosis = Age (years) – Age at diagnosis (years)
- Total muscle volume (mm^3)
  - See [Section 4.8.1](#) for definition.
- Total muscle mass (g)
  - See [Section 4.8.1](#) for definition.
- Calculated contractile muscle volume (mm^3)
  - See [Section 4.8.1](#) for definition.
- Calculated contractile muscle mass (g)
  - See [Section 4.8.1](#) for definition.
- Fat fraction (%)
- 6-minute walk distance (m)
- Time to complete 10 meter walk/run (s)

- Number and percent of patients belonging to specified CMT Type (i.e., CMT1, CMTX)
- Number and percent of CMT1 patients belonging to specified CMT1 subtype/gene mutation (e.g., CMT1A, CMT1B)
- Number and percent of CMTX patients belonging to specified CMTX subtype/gene mutation (e.g., CMTX1)
- Number and percent of patients belonging to specific forms of CMT (e.g., demyelinating, axonal, mixed)
- Number and percent of patients with first degree relatives with CMT
- Number and percent of patients who have fallen to the ground in the past 6 months
- Number and percent of patients who have had past history of fractures
- Number and percent of patients who have had past surgery for CMT
- Number and percent of patients who wears any lower limb orthotics/braces
- Number and percent of patients who uses assistive devices
- Number and percent of patients who have a regular (at least once a week) exercise program
  - For those who have a regular exercise program, the type (aerobic, resistance training, or both) and frequency of exercise program (1-2, 3-4, or 5+ times per week) will also be summarized.
- Number and percent of patients who have known nerve conduction velocity
  - For those who have a known nerve conduction velocity, the category ( $< 38$  m/s,  $\geq 38$ ) will also be summarized.
- Number and percent of patients with MRC-MMT grades belonging to the following categories: [3 to 4-], [4 to 4+], [5- to 5]
  - Summaries will be provided for each side (left and right) separately for ankle dorsiflexion, knee extension, and plantar flexion.
  - MRC-MMT grades will also be summarized (frequency with percent) by the weakest grade (left or right) for ankle dorsiflexion, knee extension, and plantar flexion.
  - MRC-MMT SCORE which represents the conversion of the MRC-MMT grade to the decimal version as follows: 5 = 5.0, 5- = 4.67, 4+ = 4.33, 4 = 4.0, 4- = 3.67, 3+ = 3.33, 3 = 3.0, 3- = 2.67, 2+ = 2.33, 2 = 2.0, 2- = 1.67, 1+ = 1.33, 1 = 1.0.
    - This will be determined for each side (left and right) and then averaged. The average will be presented in the summary table. This will be done for ankle dorsiflexion.
- Dose of ACE-083 expressed as (mg/g calculated total muscle mass)
- Dose of ACE-083 expressed as (mg/g calculated contractile muscle mass)

- CMTES2 Score
  - See [Section 4.7.1.4](#) for details on how this score is derived.
- Berg Balance Scale total score
  - See Section 4.7.1.4 for details on how this score is derived.

The table below outlines how to derive the dose of ACE-083 expressed as either mg/g total muscle, or mg/g contractile muscle:

	Dose of ACE-083 Expressed as	
	mg/g Calculated Total Muscle Mass	mg/g Calculated Contractile Muscle Mass
Bilateral Cohorts	
Step 1: For each side (right and left), compute the following: Dose injected (mg) / (Baseline CCMV {mm^3} * [1.06/1000] + Baseline CIMFV {mm^3} * [0.9/1000])
 
Step 2: Compute average of the Dose of ACE-083 expressed as mg/g total muscle for each side using the information obtained from Step 1.
	
Step 1: For each side (right and left), compute the following: Dose injected (mg) / (Baseline CCMV {mm^3} * [1.06/1000])
 
Step 2: Compute average of the Dose of ACE-083 expressed as mg/g contractile muscle for each side using the information obtained from Step 1.

CCMV = Calculated contractile muscle volume; CIMFV = Calculated intramuscular fat volume

This data will be summarized using appropriate descriptive statistics.

